4.7.4 Safety outcomes

Strokes and bleeds requiring medical assistance will be monitored and reported to the data safety monitoring board (section 6.1). Because very few of these are expected, we will rely on patient/clinician self-report and medical record review 12 months post enrollment for each participant. Should a patient not have utilization in the 3 months prior to the 12 month date, then the patient will be contacted directly for confirmation.

4.8 Follow-up Guidelines

All patients will be followed per protocol guidelines and deviations from protocol will be reported to the IRB.

Withdraw: If a patient refuses to continue to participate and they withdraw consent they will then be considered withdrawn from the study; to uphold the intention-to-treat principle, we will inquire as to whether we can continue to passively collect data from the medical record, and if ok from 10-12 month pharmacy profiles and patient surveys. If not, then no further data will be collected through medical review or self-report. Data collected prior to withdraw will be utilized unless expressly told otherwise by the patient.

Ineligible: If a patient enrolled onto the study has been found ineligible (not meeting one of the eligibility criteria) they will be documented for reason of ineligible in the study chart. These patients will continue to receive the intervention and all data will be collected for the study. This is a safe course of action as the intervention does not pose any potential harm to the patient beyond loss of privacy. The patients will be identified in the results as being ineligible and reason but will be included in all analyses.

The procedure for post-randomization exclusions will involve presenting the case to the trial PI blind to the participant's allocation and to their results.

4.9 Statistical Analysis

4.9.1 Analysis Plan

The study will be analyzed according to the *intention to treat principle (ITT)*, including all patients enrolled to the study in the arm to which they were assigned, regardless of which they were assigned to (e.g., standard care or Anticoagulation Choice + Standard Care). Reporting will include 'Per Protocol', complete data for each arm plus the ITT analysis where imputation analysis methods will be utilized to address any missing values (see section 4.9.1.1 for details on missing data analysis). Baseline characteristics will be reported in the study results with continuous values being reported as means and standard deviations and categorical values reported as counts and frequencies and compared between study arms using t-tests and chi-squared tests. Any baseline imbalances ($p < 0.05$) will be explored as a possible factor to adjust for when the outcome measures are

analyzed. We will adhere to the CONSORT guidelines to transparently report study results and ensure that sufficient information is included to allow for assessment of the study's internal and external validity.

We will use standard techniques appropriate for trials, with each outcome compared between study arms using t-tests for continuous outcomes and chi-square tests for dichotomous outcomes. If there are differences in baseline characteristics found by statistical means or found to have clinical relevance between the two study groups, these will be accounted for using regression models which include an indicator for study arm.

We will perform descriptive analyses to describe any potential heterogeneity of treatment effect (HTE) and facilitate synthesis of subgroup results in future meta-analyses. We will conduct descriptive HTE analyses by clinic (academic, community and safety net), by cohort (start or review cohort), by stroke risk (CHA₂DS₂-VASc score of 1 or ≥ 2 for men and 2 or ≥ 3 for women), and by numeracy (Less than adequate vs. not). The outcomes assessed with HTE analyses will be the same as those assessed in the trial (e.g., SDM and communication quality, knowledge, and decisional satisfaction).

For the main analyses (SDM Quality and SDM Processes), we will not assume that patient effectiveness outcomes are independent of the clinician, but rather test to see if patients seen by the same clinician have correlated outcomes. Ignoring such "clustering" effects would result in over-narrow confidence intervals and potentially false positive study results. Instead, if clustering is seen, determined by calculating the intra-class correlation ($ICC > 0.05$) for each outcome, then the value for the ICC will be reported in findings. We will use cluster (cluster at clinician level) adjusted t-test and chi-square test for comparisons between arms and hierarchical generalized linear models (HGLMs) with random main effects specified at the clinician level when adjusting by more than arm.⁵⁵ If clustering is not present then the results will reduce to a model that assumes independence and reflect findings appropriately.

Some data analysis will be conducted at the Leiden University Medical Center (the Netherlands), by using remote access connection to the Mayo server and during the appointment time on Mayo Clinic campus. All data will be stored securely on a password-protected computer. Password-protected USB drives may also be used to store electronic files in situations where connection to the Mayo server is limited or unavailable. These USB drives are encrypted and will be used in accordance with Mayo Clinic's Portable Computing and Telecommunication Devices Policy. These USB drives may be shared externally to the Leiden University Medical Center (the Netherlands).

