Data to be collected on patients include variables necessary to estimate the risk of stroke and bleeding, age, gender, BMI, smoking status, alcohol consumption, marital status, annual income of household, highest level of education, residency (nursing home), location of primary healthcare and total number of medications patients is currently taking. To further characterize the patients, we will use Chew et al single-item health literacy screener,⁴⁶ a 4-item modified Subjective Numeracy Scale,^{47, 48} and a single-item health status measure.⁴⁹

We will collect information on past use of anticoagulants through medical record review. We will categorize the patients into two cohorts for descriptive and analytical purposes. For patients who are not using an anticoagulant at the time of trial participation will form the 'Start' cohort. They may have used anticoagulation and discontinued >6 months ago, never used anticoagulation, or are using aspirin only. Patients that began an anticoagulant

within the past 10 days of the enrolled encounter that were prescribed an anticoagulant within the emergency department or an inpatient visit will still be considered a new ‘Start’.

Patients who are on warfarin or NOACs or used them in the past 6 months will form the ‘Review’ cohort. This cohort may include patients who have difficulty maintaining a therapeutic INR, or patients considering switching to a different anticoagulant or to stay on warfarin but switch to home INR monitoring.

The post consent survey for clinicians will collect demographic data (age, gender, specialty, % of their practice dedicated to anticoagulation care).

Calendar of Events

	Prior to Study Enrollment	Prior to Encounter		Post Encounter	12 months Post Enrollment
Patient Completed Forms			R A N D O M I Z E D A T I O N		
Informed Consent	X				
Pharmacy Consent	X				
Survey				X	
Phone ¹					X
Clinician Completed Forms					
Informed Consent	X				
Survey		X		X	
Clinical Data Abstracted from EMR					
Bleeds					X
Strokes					X
INR Tests (# and values outside of 2-3 range)					X
Anticoagulation Prescription		X		X	X
Pharmacist Request					
Anticoagulation					X ²

Use					
-----	--	--	--	--	--

- 1- Patients who do not have utilization within enrolling healthcare system will be contacted via phone for verification of safety data (strokes and bleeds). If no information in the record and follow-up is necessary we will call patients the maximum number allowed by the IRB followed by a postal survey

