4.9.3 Patient Allocation

Eligible patients will be allocated into either the usual care arm or to the usual care + ANTICOAGULATION CHOICE SDM tool (intervention) arm using a random sequence the trial statistician will generate *a priori*. The allocation will be stratified by clinic (academic, community or safety net), by cohort (start or review), and stroke risk (CHA₂DS₂-VASc score of 1 or ≥ 2 for men and 2 or ≥ 3 for women) using blocks of random size.

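### Section 4.9.1 picks adjustment covariates by observed baseline imbalance and names no primary model, which forgoes available precision and leaves the model open to choice

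*Combined protocol and SAP*

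**What the plan says.** The plan is in section 4.9.1 of the combined protocol and SAP. Arms are compared by default "using t-tests for continuous outcomes and chi-square tests for dichotomous outcomes". Two further provisions bring in covariates.

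- Baseline characteristics are tested between arms, and any imbalance at p<0.05 "will be explored as a possible factor to adjust for". This wording is optional.
- "If there are differences in baseline characteristics found by statistical means or found to have clinical relevance between the two study groups", these are to be handled by regression models containing an arm indicator. This wording is mandatory, and it adds a second criterion (clinical relevance) with no threshold, no named judge and no timing.

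The same section calls for "hierarchical generalized linear models (HGLMs) with random main effects specified at the clinician level when adjusting by more than arm", but lists no covariates for those models. Section 4.6 collects many candidates, among them "age, gender, BMI, smoking status, alcohol consumption, marital status, annual income of household, highest level of education". Section 4.9.3 states: "The allocation will be stratified by clinic (academic, community or safety net), by cohort (start or review), and stroke risk". Section 4.9.1 uses those three factors only for descriptive subgroup analyses and does not place them in the main comparison.

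No section says which estimate, unadjusted or adjusted, is the main result.

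**The concern.** In a randomised trial, a small baseline p-value records a chance difference. It says nothing about whether the variable predicts decisional conflict, knowledge or any other outcome. A p<0.05 trigger therefore brings in whichever variables happen to differ and usually leaves out the ones that would reduce residual variance. The precision available from data already collected is mostly not used.

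The second issue is discretion. Because one route is optional, the other rests on an undefined judgement, and no estimate is designated primary, two analysts following the text could report different arm effects. Clinicians know the allocation (4.5), the study team reviews baseline comparability monthly (6.1), and the statistical team can access the data at any time (6.4.2). The text does not say that whoever judges relevance is blind to outcomes.

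**Working it through.** **Inputs.** From 4.9.2: Decisional Conflict Scale (DCS) SD 17, detectable difference 5.2, total n=333, two-sided alpha 0.05, stated power 80%; recruitment target 999. Assumed: 1:1 allocation, independent covariates, no clustering by clinician, and R² (the share of outcome variance explained by covariates) of 5% to 30%. The documents give no R².

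**1. Reproduce the stated power.** SE = 17 × √(2/166.5) = 1.863. Power = Φ(5.2/1.863 − 1.96) = Φ(0.831) = 79.7%, which agrees with the stated 80%.

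**2. How often does chance trigger the rule?** With k independent tests, the probability of at least one p<0.05 is 1 − 0.95^k: 40% for k=10, 46% for k=12, 54% for k=15. The plan does not say how many characteristics will be tested. Counting every item listed in 4.4 and 4.6 gives about 24, hence 71%, but several are plausibly correlated, so that figure is soft. By the p<0.05 route, any one prognostic variable that is unrelated to the stratification factors is selected about 5% of the time. A stratification factor is hardly ever selected: with stratified blocks (size 4 assumed), cohort reached p<0.05 in 0 of 3,000 simulated trials.

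**3. Power for the DCS row at n=333.** Formula for prespecified adjustment: replace SD by 17 × √(1 − R²). At R² 20%, SE = 1.863 × √0.8 = 1.667 and power = Φ(5.2/1.667 − 1.96) = 87.7%. The simulations used 12 covariates and 6,000 trials per row (Monte Carlo error about 0.5 points).

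| R² | Unadjusted (sim.) | p<0.05 rule (sim.) | Prespecified, 12 covariates (sim.) | Prespecified (formula) |
|---|---|---|---|---|
| 5% | 79.7% | 79.2% | 80.3% | 81.7% |
| 10% | 79.4% | 79.6% | 82.7% | 83.7% |
| 20% | 78.7% | 79.5% | 86.3% | 87.7% |
| 30% | 79.2% | 80.3% | 90.1% | 91.6% |

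The rule moves power by about 1 point at most. The mean standard error is 1.86 unadjusted and 1.86 to 1.87 under the rule, against 1.85, 1.80, 1.70 and 1.59 prespecified. The rule does trim the sampling variance of the estimate by 0.4% to 6.5%, because it corrects the largest imbalances; prespecified adjustment trims it by 2.4% to 27.4%.

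**4. The same outcome at n=999.** SE = 17 × √(2/499.5) = 1.076. Power for 5.2 points = Φ(5.2/1.076 − 1.96) = 99.8%. The difference detectable with 80% power is (1.960 + 0.842) × 1.076 = 3.0 points unadjusted, and 3.0 × √0.8 = 2.7 points at R² 20%.

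**5. Type I error.** In null simulations at n=333 and n=999 (10 or 15 covariates, R² 10% to 30%), the rule applied mechanically rejected in about 4-5% of trials. Always reporting the better of the unadjusted and rule-adjusted results gave about 5-6%.

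**6. Omitting a stratification factor.** With a balanced factor explaining 20% of the variance, type I error was about 3.4% when it was left out of the model and 5.3% when it was included. The unadjusted test is then conservative, which is another form of lost power.

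**The case against.** The strongest reply is that the main comparison has patients to spare. Section 4.9.2 uses 333 to size one of three clinic types and sets 999 as the minimum target, and 4.9.1 calls the subgroup analyses descriptive. This stands. A reader might infer from the n=333 figures that the trial's main comparison is underpowered; step 4 shows that for 5.2 DCS points it is not.

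A second reply is that the text can be read as a sequence: an unadjusted test by default, and regression if a difference appears. That reading is possible, and it makes the p<0.05 part nearly mechanical. It does not settle what counts as clinically relevant, nor reconcile an imbalance that is only to be explored with one that is to be accounted for.

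A reader might also infer that the plan builds in a raised false-positive rate. The documents do not support this. Rates of 7.4% to 9.4% at n=333, and 6.3% to 7.5% at n=999, can be produced by searching for the smallest p-value over covariates with a standardised difference above 0.1. A search over covariates with baseline p<0.2 gives 7.6%. Neither threshold appears in the documents, and both figures require deliberate selection.

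Nor does the text say that covariates will be chosen after outcomes are seen. It implies knowledge of baseline data by arm, and neither states nor excludes sight of outcomes.

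Finally, adjustment cannot be universal. Section 4.7.4 expects very few strokes and bleeds, too few to support a model with several covariates. This also stands and limits the fix.

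**Conclusion.** The point holds as a cheap improvement in method. The p<0.05 rule selects on the wrong property and yields essentially no power gain over the unadjusted test. By formula, a prespecified set would add about 2 to 12 points of power at n=333 for R² between 5% and 30%. At n=999 it would narrow the interval, with little left to gain in power at the stated difference. The concern over inference is discretion about the model and not a built-in error: the rule as written keeps type I error at about 4-5%, and reporting the better of two results would take it to about 5-6%.

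The size of the gain rests on the assumed R², independent covariates and no clinician clustering. The gain from the clinical-relevance route cannot be computed, because its criterion is undefined. That the p<0.05 rule adds essentially no power holds across the whole range tried.

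**What to change.** In 4.9.1, delete the baseline significance tests and the imbalance trigger; keep the descriptive baseline table. Before outcomes are examined:

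- For each SDM quality and SDM process outcome, and for anticoagulation use, name one primary model.
- Include in it a short set of covariates chosen for expected association with the outcome, together with the stratification factors (clinic, cohort, stroke risk), whatever the observed balance. Cohort already captures prior anticoagulant use, so that need not be added separately.
- Restrict the set to variables measured before the encounter. The calendar in 4.6 places the patient survey after the visit, and the text lets only part of it be completed earlier, so the timing of any survey item should be confirmed before it is used.
- State the effect measure for binary outcomes, since covariate adjustment in a logistic model changes the quantity estimated.
- Report the unadjusted result, and any adjustment prompted by an observed imbalance, as labelled sensitivity analyses.
- Leave strokes and bleeds unadjusted.

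The cost is mainly wording, because the variables are already being collected. The team must commit to the list early and must handle some missing covariate values. Section 4.9.1 promises imputation and refers to 4.9.1.1 for details, but that section gives no imputation method, so one has to be stated.

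### The planned arm comparisons leave out the three factors used to stratify randomisation, and the baseline p<0.05 rule will almost never bring them in

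*Combined protocol and SAP*

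**What the plan says.** Section 4.9.3 (Patient Allocation): "The allocation will be stratified by clinic (academic, community or safety net), by cohort (start or review), and stroke risk", "using blocks of random size". With three clinic types, two cohorts and two stroke-risk levels, that makes 12 strata.

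Section 4.9.1 (Analysis Plan) describes the arm comparison as "with each outcome compared between study arms using t-tests for continuous outcomes and chi-square tests for dichotomous outcomes". For SDM quality and SDM process outcomes it adds a clinician-level correction "if clustering is seen, determined by calculating the intra-class correlation" (threshold 0.05). That correction is either cluster-adjusted versions of the same tests or "hierarchical generalized linear models (HGLMs) with random main effects specified at the clinician level when adjusting by more than arm". No stratification factor is named in any of these.

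The stratifiers appear in the analysis only here: "We will conduct descriptive HTE analyses by clinic (academic, community and safety net), by cohort (start or review cohort), by stroke risk".

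Covariates come in by what the baseline table shows. A variable with p<0.05 between arms "will be explored as a possible factor to adjust for when the outcome measures are" analysed. Differences found statistically or thought clinically relevant are handled as follows: "these will be accounted for using regression models which include an indicator for study arm".

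**The concern.** Stratified blocks remove most of the between-stratum variation from the difference between arms. A plain t-test or chi-square test still counts that variation in its standard error. The interval is then wider than the design warrants, and the test rejects less often than its nominal 5%.

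The adjustment rule does not repair this. It looks for imbalance, and the stratifiers are the variables that the design has balanced. Variables outside the stratification are selected by chance, whether or not they predict the outcome. The covariate list is also settled only after the baseline data have been seen, with one criterion (clinical relevance) left undefined.

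At stake are some precision, some power for persistence, and a covariate set fixed in advance. Validity is not at stake.

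**Working it through.** **Inputs from the documents (section 4.9.2).** Decisional Conflict Scale (DCS): SD 17, detectable effect 5.2, 80% power at 333 patients. Recruitment target 999. Persistence: about 765 records, 60% v 69% (read here as proportions of patients), 80% power. Two-sided alpha 0.05.

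**Assumptions.** The share of outcome variance explained by the strata (R²) is not given; 0, 5% and 10% are shown. Arms are equal, there is no clinician clustering, and the normal approximation is used. Block sizes are not given; 2, 4 and 6 are assumed.

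**1. The plan's own figures.**
- DCS at 333: SE = 17 × 2/√333 = 1.863; 5.2/1.863 = 2.79; power = Φ(2.79 − 1.96) = 79.7%. The stated 80% reproduces.
- Persistence: SE = √[(0.60×0.40 + 0.69×0.31)/382.5] = 0.0344; z = 0.09/0.0344 = 2.613; power = Φ(2.613 − 1.96) = 74%, not the stated 80%. That gap is a separate matter and is not caused by the omitted strata, but it is the starting point below.

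**2. SDM outcomes at 999.** With the strata balanced, the true SE is the nominal SE × √(1−R²).

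| R² | Unadjusted SE too large by the factor 1/√(1−R²) | Type I error, P(\|Z\| > 1.96/√(1−R²)) | DCS half-width, unadjusted | DCS half-width, adjusted |
|---|---|---|---|---|
| 0 | 1.000 | 5.0% | 2.11 | 2.11 |
| 5% | 1.026 | 4.4% | 2.11 | 2.06 |
| 10% | 1.054 | 3.9% | 2.11 | 2.00 |

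The unadjusted half-width is 1.96 × 17 × 2/√999 = 2.11. In sample-size terms, R² of 5% or 10% is worth 999/0.95 = 1,052 or 999/0.90 = 1,110 patients. For the five tabulated effects, z at 999 is 4.83-4.96, so power is above 99.7% either way.

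Simulation of stratified blocks (6,000 runs per R², Monte Carlo SE about 0.3 points) gave DCS type I error of 5.0/4.3/3.5% unadjusted and 5.0/4.8/4.5% adjusted.

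**3. Persistence.** Records are missing for f = 1 − 765/999 = 0.234. If they are lost at random, balance is only partly kept, and the true-to-nominal variance ratio of the unadjusted difference is k = 1 − R²(1−f).

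| R² | k | SE factor 1/√k | Type I error | Power unadjusted, Φ((2.613−1.96)/√k) | Power adjusted, Φ(2.613/√(1−R²)−1.96) |
|---|---|---|---|---|---|
| 0 | 1.000 | 1.000 | 5.0% | 74.3% | 74.3% |
| 5% | 0.962 | 1.020 | 4.6% | 74.7% | 76.4% |
| 10% | 0.923 | 1.041 | 4.1% | 75.2% | 78.6% |

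Simulated power was 74.9/75.6/75.5% unadjusted and 75.1/77.9/79.4% adjusted (Monte Carlo SE about 0.6 points).

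**4. How large R² could be.** One evenly split two-level factor reaches R² = 10% only with a DCS gap between strata of 2 × 17 × √0.10 = 10.8 points, or a persistence gap of 2 × √(0.645×0.355) × √0.10 = 30 percentage points. So 10% is a generous upper end.

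**5. The p<0.05 trigger.**
- With blocks of at most 6, a stratum can end at most 3 patients out of balance. A two-level factor has 6 strata per level, so the worst case is 18 patients per level, in opposite directions.
- With about 500 patients per level, that is 259 v 241 and 241 v 259: chi-square = 4 × 9²/250 = 1.30, p = 0.25.
- If one level holds only 15% of patients: 2 × 81/75 + 2 × 81/425 = 2.54, p = 0.11. Neither worst case reaches 0.05.
- In 3,000 simulated allocations of 999 (low-stroke-risk share 15% or 50%), no stratifier reached p<0.05, and the smallest p was 0.53. An unstratified 50/50 variable did so in 3.9% and 5.0%.

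**The case against.** The strongest reply is that little is lost. No bias or excess of false positives is alleged, the tabulated outcomes have ample power at 999, and the effect depends on an R² that the documents do not supply. If the gap between strata were only as large as the trial's own target effects, the gain nearly vanishes. A 5.2-point DCS gap gives R² = (5.2/34)² = 2.3% and a half-width of 2.08 instead of 2.11. A 9-point persistence gap gives R² = 0.9% and power of 74.7% instead of 74.4%. This is fair. It places the likely benefit towards the lower part of the range, although several factors together could explain more.

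Second, variation by clinic type may show up as clinician clustering. If each clinician works in one clinic type and clinic type alone explains 10% of variance, simulation with 60-240 clinicians (assumed) puts the intra-class correlation above 0.05 in 96-99% of trials, and in about half at 5%. The plain t-test would then often not be the analysis used. This narrows the upper end for SDM outcomes. It does not reach cohort or stroke risk, which are patient-level, nor persistence, because section 4.9.1 confines the clustering rule to SDM quality and processes.

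Third, records may not be lost at random. The 765 already excludes the roughly 10% expected not to start or continue medication, and that decision comes after randomisation and may differ by cohort. The top-end gain of 3 to 4 power points is therefore not secure.

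Fourth, section 4.9.1 also allows adjustment for clinically relevant differences. It does, but near-exact balance makes that route unlikely for the stratifiers, and the criterion is undefined.

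**Conclusion.** The point holds. The stratifiers are absent from every planned arm comparison, and the p<0.05 rule will in practice not select them. That second conclusion needs no assumption about R², only modest block sizes.

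The cost is small and conservative. Over R² of 0-10%, it runs from nothing to intervals about 5% too wide for SDM outcomes, and from nothing to about 3.5 percentage points of power for persistence. Both ranges assume no clinician clustering, and the persistence range also assumes random loss of records; departures from either would mainly reduce the upper end. Conclusions from the planned tests would remain valid. The case for change is that the improvement is almost free and that it replaces a data-driven covariate choice with a fixed one.

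**What to change.** In section 4.9.1:

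- Pre-specify, as the main analysis of every outcome, a comparison adjusted for clinic type, cohort and stroke-risk stratum as main effects.
- Continuous outcomes: use a linear model.
- Dichotomous outcomes: make a stratified (Mantel-Haenszel) or standardised risk difference the main measure, which matches the rate differences used in section 4.9.2.
- Leave the clinician-clustering rule and its 0.05 threshold as they are. Where the hierarchical model is used for a dichotomous outcome, derive the standardised risk difference from it.
- Remove baseline p<0.05 as a reason to adjust, name any further covariate in advance, and report the baseline table descriptively.
- Keep the planned unadjusted or cluster-adjusted tests as sensitivity analyses.

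The cost is SAP wording and some extra programming. No new data are needed, because the allocation already requires all three factors for each patient.

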4.7.3 Anticoagulation Use

Rate of anticoagulation: The key indicator of the choice to start an anticoagulant will be its prescription in the EMR prescription module (observed discussions and patient/clinician accounts may not reflect decisions confirmed after the visit with a prescription, for example, after the clinician or the patient checked other information or with other informants). After this primary ‘decided as prescribed’ approach, we will conduct secondary analyses using patient/clinician reported and video-observed decisions. Decisions may be for starting or not an anticoagulant in the start cohort. It is possible that there may be some decisions to stop anticoagulation in the review cohort, but we expect start and review cohorts to contribute information about choice of anticoagulant.

Choice of anticoagulant: We will review the EMR and 10-month pharmacy profiles (to stand for the 12-month profile given the automatic expiration of pharmacy records at 1 year) to determine the prescribed anticoagulant and whether and when switches to another agent or to no anticoagulant took place.

Together, they should capture choice and switches even when these occur as a result of changes in clinician (e.g., from cardiology to primary care). When available, we will note the documented reasons from clinical notes for choosing and switching as well as with which clinician the change was made (e.g primary, cardiology, etc.).

Anticoagulation persistence: Patients will identify the pharmacy(-ies) they use to fill their prescriptions and authorize us to obtain their prescription drug fill data. We will calculate anticoagulation persistence, using the percent days covered (PDC) based on prescription refill behaviors (total days supply of anticoagulant filled / total days of observation from the first prescription fill date; range 0-100%). We will also pull all pharmacy refills for the 12 months prior to enrollment. This will allow us to calculate persistence for prior use of anticoagulants for the review cohort to compare to persistence post encounter and see if there is an impact.

Warfarin use: For patients who choose to stay on warfarin, we will also use as secondary measures of adherence: (a) the proportion of INR tests obtained/scheduled; and (b) percentage of time at therapeutic target (typically INR 2-3).

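### The Aim 2 arm comparisons leave out the patient's own baseline agent and prior persistence, which the trial already collects; the tests are valid, but Review-cohort precision is given away

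*Combined protocol and SAP*

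**What the plan says.** Section 4.9.1 sets one default for all outcomes: "each outcome compared between study arms using t-tests for continuous outcomes and chi-square tests for dichotomous outcomes". If baseline differences between the arms are found statistically or judged clinically relevant, "these will be accounted for using regression models which include an indicator for study arm". No baseline value of any outcome is named as a covariate in advance. The hierarchical model later in 4.9.1 is for SDM quality and processes and names no baseline covariate either.

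The baseline values are collected. Section 4.6 states: "We will collect information on past use of anticoagulants through medical record review". Its Calendar of Events schedules abstraction of the anticoagulation prescription before the encounter. The Review cohort consists of "Patients who are on warfarin or NOACs or used them in the past 6 months". For persistence, 4.7.3 states: "We will also pull all pharmacy refills for the 12 months prior to enrollment". The purpose given is to "calculate persistence for prior use of anticoagulants for the review cohort to compare to persistence post encounter and see if there is an impact".

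The choice outcome in 4.7.3 uses the medical record and pharmacy profile to "determine the prescribed anticoagulant and whether and when switches to another agent or to no anticoagulant took place". Section 4.9.3 stratifies allocation by clinic, by Start or Review cohort, and by stroke risk. None of these separates a warfarin user from a NOAC user, or a patient with good prior persistence from one with poor persistence.

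**The concern.** Many Review patients can be expected to leave the visit on the agent they came in on. Much of the variation in the agent held afterwards is then fixed before randomisation, and a crude chi-square test counts it as noise. Entry agent would remove that noise, but the plan brings it in only if the arms happen to differ. Adjusting for the randomisation strata would not help, because entry agent is not one of them.

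The same argument applies more weakly to PDC. Prior PDC should predict later PDC in Review patients. Section 4.7.3 plans to set one against the other, but does not say whether this is a within-patient change, a contrast between arms, or a covariate.

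At stake is how sharply the trial can describe what the tool does to agent and persistence in patients already treated.

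**Working it through.** **Agent held after the visit, Review cohort.** The documents give no entry shares or switching rates, so these are assumptions. The even Start/Review split in 4.9.2, applied to 999 patients, gives about 500 Review patients, or 250 per arm. Half are on a NOAC at entry and 95% of those stay on one in both arms. Of warfarin users, 10% move to a NOAC in control and 25% with the tool.

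- Share on a NOAC afterwards: control 0.5 × 0.95 + 0.5 × 0.10 = 0.525; tool 0.5 × 0.95 + 0.5 × 0.25 = 0.600; difference 0.075.
- Crude: SE = √[(0.525 × 0.475 + 0.600 × 0.400)/250] = 0.0442. Power = Φ(0.075/0.0442 − 1.96), about 40%.
- Stratified by entry agent: within-stratum variance is 0.5 × 0.0475 + 0.5 × 0.0900 = 0.0688 in control and 0.5 × 0.0475 + 0.5 × 0.1875 = 0.1175 with the tool. SE = √[(0.0688 + 0.1175)/250] = 0.0273. Power = Φ(0.075/0.0273 − 1.96), about 78%.

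**A switch, counted from the entry agent.** Same scenario, plain chi-square test on switched yes or no.

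- Control 0.5 × 0.05 + 0.5 × 0.10 = 0.075; tool 0.5 × 0.05 + 0.5 × 0.25 = 0.150; difference again 0.075.
- SE = √[(0.075 × 0.925 + 0.150 × 0.850)/250] = 0.0281. Power = Φ(0.075/0.0281 − 1.96), about 76%.

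Simulation of 20,000 trials per scenario (Pearson tests against a Cochran-Mantel-Haenszel test stratified by entry agent) agrees:

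| Warfarin users switching | Agent held, crude | Agent held, stratified | Switch yes/no, crude |
|---|---|---|---|
| 10% v 25% | 40% | 78% | 76% |
| 10% v 20% | 21% | 47% | 46% |
| 20% v 35% | 40% | 67% | 62% |

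With no effect (10% v 10%), both the crude and the stratified test of agent held reject about 5% of the time.

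Sensitivity: over entry NOAC shares of 30% to 70% and control switching of 10% to 20%, stratifying cuts the variance for agent held by about 39% to 66%. A separate simulation with equal switching in both directions, 191 per arm and 30% or 50% on the agent class at baseline multiplies the SE by 0.43–0.45 if 5% switch, 0.60–0.64 if 10% switch, and 0.79–0.82 if 20% switch.

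**Persistence.** Inputs from 4.9.2: 999 × 0.90 × 0.85 = 764, which matches the plan's figure of about 765 records; 60% v 69%, read as proportions; two-sided 0.05. With 382.5 per arm and mean proportion 0.645:

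- SE under no difference = √(2 × 0.645 × 0.355/382.5) = 0.0346; SE under the alternative = √[(0.60 × 0.40 + 0.69 × 0.31)/382.5] = 0.0344.
- Power = Φ[(0.09 − 1.96 × 0.0346)/0.0344], about 74%. The plan states 80%, which would need 443 per arm (886 records). That gap is a separate matter; 74% is the baseline used here.
- Let ρ be the correlation between prior and later PDC (not given in the documents). Prior PDC helps only the Review half, so the variance is multiplied by 1 − 0.5ρ².

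| ρ | Variance factor | Power, all records | Power, Review only (191 per arm) |
|---|---|---|---|
| none | 1 | 74% | 45% |
| 0.3 | 0.955 | 76% | 49% |
| 0.5 | 0.875 | 80% | 56% |
| 0.7 | 0.755 | 85% | 73% |

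The Review-only column uses the factor 1 − ρ². These gains are on the mean or risk-difference scale; the SE of a log odds ratio does not shrink in this way.

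**The case against.** The strongest reply is that 4.7.3 includes switching in the choice outcome. If a switch is counted from the entry agent, the baseline is already built into the outcome, and the table shows little left to gain: about 0 to 5 points across entry NOAC shares of 30% to 70%. A reader might infer from the 40% v 78% contrast that the plan would miss a real movement between agents. The documents do not support that for switching. Two limits remain: 4.7.3 does not state the reference point for a switch, and the comparison assumes equal NOAC retention in both arms.

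Four further replies stand in whole or in part.

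- A reader might infer that prior persistence goes unused. It does not: 4.7.3 plans a prior-to-later comparison in the Review cohort. What is missing is its link to an arm contrast.
- A reader might infer that any chance imbalance in entry agent passes into the result. The rule in 4.9.1 would catch a marked one. At 250 per arm, a difference of up to 1.96 × √(2 × 0.25/250) = 8.8 points would not reach p < 0.05, and adjustment would then depend on a judgement of clinical relevance.
- Aim 2 is worded as descriptive in section 1.0, the primary endpoint is SDM quality, and 4.9.2 makes no power claim for choice of agent. The unadjusted tests are unbiased under randomisation, so this point touches neither the primary analysis nor the error rate.
- Entry agent need not be known for every Review patient. The cohort includes people who stopped within 6 months, and 4.2.3 lets patients decline release of outside records.

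**Conclusion.** The point holds as one of efficiency. The default comparison omits a baseline value that the trial already has, and randomisation does not balance it. The gain from using it is large only for the crude comparison of agent held in the Review cohort: about 40% to 78% power in the scenario shown, under assumed entry shares, retention and switching rates. For switches counted from the entry agent it is small. For persistence it is modest, from 74% to between 76% and 85% over the assumed range of ρ. The documents do not show that precision is lost to this extent in practice, since they give neither a correlation nor a switching rate, and they do not support reading this as bias or as a fault in the primary analysis. The change is still worth making: it needs no new data and settles the adjustment before outcomes are seen.

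**What to change.** Add to 4.9.1:

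1. For agent held after the visit in the Review cohort (for example NOAC or not), compare arms with a Mantel-Haenszel test and risk difference stratified by agent at entry: none or stopped, warfarin, NOAC. Define a switch as a change from the entry agent.
2. For post-encounter PDC, compare arms on the mean or risk-difference scale with pre-enrolment PDC as a covariate in Review patients, a Start/Review indicator so that Start patients are kept, and a missing indicator where prior fills cannot be obtained. State that this is the form the prior-to-later comparison in 4.7.3 takes. A covariate suits better than a raw change score, because the prior window is 12 months and the later one 10.
3. Report the crude comparisons alongside.

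The cost is a few sentences and slightly more analysis work. No visit, form or data request is added. If many prior fills cannot be retrieved, the PDC gain will be smaller than shown.
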